RESEARCH STUDY PROTOCOL

1. Project Summary

Background: Endoscopic retrograde cholangiopancreatography (ERCP) is a procedure used to diagnose and treat problems in the bile and pancreatic ducts. One common issue it addresses is stones in the common bile duct. However, ERCP can be risky and may lead to complications like pancreatitis, bleeding, perforation, and infections. Infections can occur in 5% to 18% of cases and are responsible for about 7.8% of deaths related to ERCP complications. To reduce infection risks, some methods have been suggested, such as using fewer contrast injections, lowering bile duct pressure, ensuring complete drainage, and using preventive antibiotics. However, the use of preventive antibiotics is debated because it can lead to antibiotic resistance, which is a growing global problem. Major medical societies recommend antibiotics only in specific cases, but the evidence supporting this is not strong. This study aims to find out if using preventive antibiotics can lower infection rates after ERCP in patients with bile duct stones.

Study aims: we designed this study to evaluate whether prophylactic antibiotic use can reduce infectious complications after ERCP in patients with common bile duct stones.

Methods: This study is expected to be conducted from December 2022 to December 2025 at 108 Military Central Hospital, Hanoi, Vietnam. Participants will be patients with bile duct stones who need ERCP but do not have cholangitis. They will be randomly assigned to one of three groups: Prophylactic Antibiotic Group: Will receive Amikacin (an antibiotic) before the ERCP procedure. Full-dose Antibiotic Group: Will receive Amikacin and a third-generation cephalosporin antibiotic from before the ERCP until hospital discharge. Control Group: Will not receive antibiotics, only normal saline. After ERCP, patients will be monitored for signs of infection through symptoms and lab tests.

Outcomes: Primary Outcome: Infectious Complications post-ERCP. Secondary Outcomes: Cholangitis, Cholecystitis, Bacteremia and Inflamatory markers.

2. General information

Study Title

Does Prophylactic Antibiotics Reduce Infectious complications Post Endoscopic Retrograde Cholangio Pancreatography in Common Bile Duct Stones Patients: A Clinical Trial?

Principal Investigator

- 1. [name] [name]
- 2. [name] [name]

Study Site: 108 Military Central Hospital

3. Rationale and Background Information

Endoscopic Retrograde Cholangiopancreatography (ERCP) is an important method for diagnosing and treating biliary and pancreatic diseases, among which common bile duct stones are one of the most frequently encountered causes. However, ERCP is an invasive procedure with a high risk of complications, including acute pancreatitis, bleeding, hollow organ perforation, and infection. Among these, infectious complications occur in approximately 5% to 18% of cases and account for around 10% of ERCP-related mortality¹⁻³.

To minimize the risk of infection, several strategies have been proposed, such as limiting the injection of contrast into the bile duct, aspirating bile to reduce biliary pressure, ensuring complete biliary drainage, and using prophylactic antibiotics⁴. However, the clinical effectiveness of prophylactic antibiotic use remains controversial. A meta-analysis by Cochrane et al. (2010) showed that prophylactic antibiotics can reduce the risk of bacteremia and cholangitis⁵. In contrast, a more recent meta-analysis by Maria Fernanda Shinin Merchan (2022), along with several other studies, suggested that prophylactic antibiotics may reduce

the rate of bacteremia but do not significantly decrease the incidence of cholangitis, sepsis, post-ERCP pancreatitis, or mortality⁶⁻⁸.

Rational antibiotic use remains a significant challenge for clinicians, as broad-spectrum antibiotic treatment can lead to unnecessary costs and contribute to the growing problem of antibiotic resistance—a serious global health concern causing approximately 700,000 deaths annually and an estimated economic burden ranging from 1 to 3.4 trillion USD. This figure continues to rise⁹⁻¹¹.

According to guidelines from major organizations such as the American Society for Gastrointestinal Endoscopy (ASGE) and the European Society of Gastrointestinal Endoscopy (ESGE), routine prophylactic antibiotic use is not recommended, except in cases of incomplete biliary drainage or in immunocompromised patients. However, these recommendations are based on low-quality evidence and remain weak in strength.

Therefore, we designed this study to evaluate whether prophylactic antibiotic use can reduce infectious complications after ERCP in patients with common bile duct stones.

4. Objectives

To evaluate whether prophylactic antibiotic use can reduce infectious complications after ERCP in patients with common bile duct stones.

5. Study Design

Interventional Study, open-label, randomized controlled trial.

6. Methodology

- Eligibility

Participant inclusion criteria:

- Patients ≥ 18 years with common bile duct stones are diagnosed by abdominal ultrasound, endoscopic ultrasound, CT scan, or abdominal MRI.
 - No signs of cholangitis at the time of admission, defined by the following criteria:
 - + Non fever (temperature $< 37^{\circ}$ C)
 - + White blood cell count between 4 G/L and 10 G/L
 - Good general condition, classified as ASA Physical Status I or II

Participant exclusion criteria:

• Patients with severe coagulopathy (INR > 1.5 or platelet count < 50 G/L)

Patients with severe systemic illnesses, such as unstable myocardial infarction, respiratory failure, or circulatory failure

- Patients with duodenal perforation or failed ERCP due to inability to access the papilla
- Patients with active infections in other organ systems requiring antibiotic therapy
- Patients have received any systemic antibiotics within 48 hours prior to the ERCP procedure
 - Patients are allergic to antibiotics used in the study.

- Interventions

Patients with common bile duct stones without signs of cholangitis at the time of hospital admission. Patients have an indication for ERCP stone extraction and randomly assigned to one of three study groups by using a simple randomization method in which the remainder of their record number divided by 3 determined the group allocation.

- •Control Group: No Antibiotics Group (Group 1)
- + Medication: normal saline
- + Administration: No antibiotics administered. Patients will receive an intravenous infusion of normal saline on the day of the procedure.
 - •Prophylactic Antibiotic Group (Group 2)
 - + Medication: Amikacin
- + Administration: Amikacin at a dose of 15 mg/kg, diluted in 0.9% NaCl to a total volume of 100mL, administered via intravenous infusion over 60 minutes

+ Timing: Administered 60 minutes before ERCP procedure. For patients with renal impairment,

the Amikacin dose will be adjusted based on glomerular filtration rate (GFR).

- + Other Names: Antibiotic prophylaxis
- •Full-dose Antibiotic Group (Group 3)
- + Medication: Amikacin + Third-generation Cephalosporine
- + Administration: Amikacin at 15 mg/kg/day in combination with Cefoperazone 2 g twice daily, administered by slow intravenous injection every 12 hours
- + Timing: From before the ERCP procedure until hospital discharge, typically lasting 4–7 days.

After undergoing ERCP, patients will be monitored for signs of infectious complications through clinical symptoms and laboratory tests within 24 to 48 hours post-procedure.

Clinical symptoms include: pulse, blood pressure, consciousness, abdominal pain, fever, jaundice, and melena.

Laboratory tests include: complete blood count and blood biochemistry (urea, creatinine, GOT, GPT, GGT, ALP, total bilirubin, direct bilirubin, CRP, procalcitonin, amylase, lipase).

Patients with high fever > 38°C will undergo blood culture and abdominal CT scan if necessary.

Patients with complications will be monitored clinically, undergo laboratory tests, and receive treatment according to guidelines until they are stable and discharged from the hospital.

[figure not shown]
Outcomes

• Primary Outcome:

Infectious Complications post-ERCP: Fever > 38°C occurring within 24 to 48 hours following ERCP. ¹²

- Secondary Outcomes:
- + Cholangitis: worsening right upper quadrant abdominal pain; fever (ear temperature >38.0 °C); evidence of systemic inflammation: either elevated white blood cell count (>10 G/L) or increased C-reactive protein levels (>10 mg/L), or a further rise if already above the upper normal limit (UNL) prior to ERCP; and indicators of hepatobiliary dysfunction—such as jaundice (total bilirubin >2.0 mg/dL, or worsened if pre-existing), or elevated liver enzymes (GGT, ALP, AST, ALT >1.5×UNL, or further increased if already above UNL before the procedure)¹³.
- + Cholecystitis: Diagnosis was made according to the criteria of the Tokyo Guidelines 2018(TG18)¹³.
 - + Inflamatory markers: WBC, CRP, Procalcitonin
 - + Bacteremia: Positive blood culture for bacteria¹⁴
 - Other Outcomes:
- + Bleeding: Bleeding observed during the procedure or clinical signs such as melena, anemia, and a decrease in hemoglobin level exceeding 2 g/dL^{15} .
 - + Pancreatitis: Diagnosis based on the Revised Atlanta Classification (2012)¹⁶

- Study flowchart

3. Safety considerations

Patients who show signs of infection after undergoing ERCP will be treated with antibiotics according to the Tokyo Guidelines 2018 and the recommendations of the Vietnamese Ministry of Health until they are stable and discharged from the hospital.

Patients who develop other complications such as acute pancreatitis or gastrointestinal bleeding will be treated according to the respective protocols for acute pancreatitis and gastrointestinal bleeding until they are stable and discharged.

Patients who experience duodenal perforation during ERCP will be withdrawn from the study and treated with endoscopic clip placement or surgery.

Patients who are admitted while awaiting ERCP and develop signs of infection with a fever >37°C will be withdrawn from the study and treated with antibiotics according to the Tokyo Guidelines 2018 and the recommendations of the Vietnamese Ministry of Health

4. Follow-up

Participants will be followed for 7 days after the ERCP procedure to monitor for adverse events, including post-ERCP pancreatitis, cholangitis, bleeding, or gastrointestinal perforation. Monitoring will be performed through daily clinical assessments during hospitalization, supported by laboratory tests (Ure, Creatinin, GOT, GPT, GGT, ALP, total bilirubin, direct bilirubin, CRP, procalcitonin, amylase, lipase and CT scan as needed) and vital signs.

For participants discharged before day 7, follow-up will continue via telephone to assess health status and identify any signs or symptoms suggestive of post-procedural complications. If concerning symptoms are reported, participants will be advised to return for medical evaluation.

All adverse events (AEs) and serious adverse events (SAEs) will be documented, managed appropriately, and reported in accordance with the study's safety protocol. Follow-up will conclude at day 7 post-ERCP unless complications arise, in which case follow-up will continue until resolution.

5. Data management and statistical analysis

- Data Management:

Study data will be collected using paper-based Case Report Forms (CRFs) and subsequently entered manually into a Microsoft Excel spreadsheet designed by the research team. Each participant will be assigned a unique study identification number (ID) to maintain confidentiality. The dataset will be encrypted and stored on a password-protected computer with access restricted to authorized study personnel.

- Statistical analysis

Data analysis will be performed using SPSS version 22.

• Descriptive analysis

Quantitative variables will be presented as mean and standard deviation if normally distributed, or as median and interquartile range if not normally distributed.

Qualitative variables (e.g., gender, rate of cholangitis, etc.) will be presented as frequency and percentage.

• Comparison between groups

Categorical variables (e.g., rate of cholangitis, mortality rate, etc.) will be compared among the three groups using the Chi-square test. If expected cell counts are small, Fisher's exact test will be used.

Continuous variables (e.g., length of hospital stay, biochemical indices, etc.) will be compared using one-way ANOVA if the data are normally distributed, or the Kruskal-Wallis test if not.

If statistically significant differences are found among the three groups, post-hoc analyses will be conducted to determine which group pairs differ. Differences between groups will be assessed using Relative Risk (RR) along with a 95% Confidence Interval (95% CI). A p-value of less than 0.05 will be considered statistically significant.

• Sample Size Calculation

The sample size was calculated using G*Power software (version 3.1), applying a Chisquare test (goodness-of-fit test) with the following parameters: significance level (α) = 0.05, power (1 – β) = 0.80, and a medium effect size (w = 0.3) as recommended by Cohen¹⁷. This yields a total sample size of 108 participants (36 per group) for a chi-square goodness-of-fit test with 2 degrees of freedom.

6. Quality assurance

The study will be conducted in accordance with ethical regulations for biomedical research involving human participants and has been approved by the Institutional Ethics Committee.

To ensure quality and consistency throughout the implementation process, the research team has developed standard procedures for all steps, including patient selection, intervention, data collection, and data processing.

Monitoring of adverse events, as well as ensuring the integrity and safety of participants, will be jointly conducted by the research team members, the principal investigator, and the hospital's Ethics Committee.

7. Expected outcomes of the study

The study is expected to provide scientific evidence on the effectiveness of prophylactic antibiotic use in preventing post-ERCP infections in patients with common bile duct stones. This may contribute to improving clinical practice guidelines, optimizing antibiotic use, and reducing the risk of antibiotic overuse and resistance

8. Dissemination of results and publication policy

Results will be submitted to peer-reviewed journals and presented at scientific meetings. Participants will be informed of the study outcomes upon request

9. Duration of the Project

The study is expected to be conducted from December 2022 to December 2025

10. Project management

The principal investigator will be responsible for the overall management and coordination of the project, including protocol adherence, data collection, data analysis, and reporting.

11. Ethical Considerations

This study has been reviewed and approved by the Institutional Ethics Committee. All participants will provide written informed consent prior to any study procedures.

12. Monitoring and Adverse Events Reporting

Adverse events and serious adverse events will be recorded and reported to the Ethics Committee according to institutional guidelines.

References

- 3. Özcan Ö, Arikan S. Determining the Risk Factors of Complications Due to Endoscopic Retrograde Cholangiopancreatography. *Cureus*. Jan 2024;16(1):e51666. doi:10.7759/cureus.51666
- 4. Wobser H, Gunesch A, Klebl F. Prophylaxis of post-ERC infectious complications in patients with biliary obstruction by adding antimicrobial agents into ERC contrast media- a

- single center retrospective study. *BMC gastroenterology*. Jan 13 2017;17(1):10. doi:10.1186/s12876-017-0570-4
- 6. Merchan MFS, de Moura DTH, de Oliveira GHP, et al. Antibiotic prophylaxis to prevent complications in endoscopic retrograde cholangiopancreatography: A systematic review and meta-analysis of randomized controlled trials. *World journal of gastrointestinal endoscopy*. Nov 16 2022;14(11):718-730. doi:10.4253/wjge.v14.i11.718

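### Immunocompromised patients, whom the guidelines cited in the protocol except from the advice against prophylaxis, can still be allocated to saline because no eligibility criterion names them

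*Protocol*

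**What the plan says.** Protocol section 3 (Rationale and Background Information) reports the ASGE and ESGE position that "routine prophylactic antibiotic use is not recommended, except in cases of incomplete biliary drainage or in immunocompromised patients". It then comments that "these recommendations are based on low-quality evidence and remain weak in strength" and gives this as the reason for the trial.

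In section 6 (Methodology, Eligibility), three criteria bear indirectly on immune status:

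- "White blood cell count between 4 G/L and 10 G/L", listed as part of the definition of no cholangitis at admission;
- "Good general condition, classified as ASA Physical Status I or II", with no rule for how the grade is assigned;
- the exclusion "Patients with severe systemic illnesses, such as unstable myocardial infarction, respiratory failure, or circulatory failure".

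The exclusion list also covers two situations that concern antibiotics directly: "Patients with active infections in other organ systems requiring antibiotic therapy" and "Patients are allergic to antibiotics used in the study". No criterion names immunocompromise or immunosuppressive treatment.

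Under Interventions in the same section, "the remainder of their record number divided by 3 determined the group allocation". Group 1 receives saline and no antibiotic.

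The safeguards apply to all participants. Section 6 has clinical and laboratory monitoring at 24 to 48 hours, with blood culture for fever above 38°C. The later section 3 (Safety considerations) has antibiotics once signs of infection appear after ERCP, and withdrawal with treatment for fever before it. The later section 4 (Follow-up) has follow-up to day 7.

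**The concern.** The protocol itself identifies a group for whom the guidelines it relies on make an exception, and then leaves that group's eligibility to criteria written for other purposes. The other exception, incomplete drainage, becomes known only during or after ERCP. Immune status can be checked before allocation, so the gap could be closed at screening.

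What is at stake is the safety of a few patients at most. Followed as written, the plan can withhold prophylaxis from someone in an excepted group, and cover in Group 1 begins only when infection shows. The protocol does not contradict itself, since reporting a guideline does not bind the trial to follow it. The group that would be exposed is also too small for a trial of 36 per arm to learn anything useful about it.

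**Working it through.** **1. Do the listed criteria remove the group?** Take a stable patient on immunosuppressive medication, with no fever and a normal white count.

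| Criterion (section 6, Eligibility) | Does it remove this patient? |
|---|---|
| White count 4 to 10 G/L | No. It removes leukopenic patients, but only as a by-product of the cholangitis definition. |
| ASA I or II | Not if the investigator grades ASA II. The protocol does not define the grading or link it to immune status. |
| Severe systemic illness | Not clearly. The list is open-ended, but its examples are cardiac, respiratory and circulatory. |
| Active infection elsewhere needing antibiotics | No, if there is none. |
| Systemic antibiotics in the 48 hours before ERCP | No, if there were none. |
| Allergy to the study antibiotics | No, if there is none. |

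The remaining criteria (age, stones on imaging, coagulopathy, perforation or failed access to the papilla) do not concern immune status. The patient is eligible, and allocation by record number makes no exception.

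**2. Is there a justification or safeguard for this group?** The weak-evidence remark in section 3 covers the recommendations as a whole. The monitoring, treatment, withdrawal and follow-up rules apply to everyone alike. None sets an earlier check, a lower threshold or a different treatment for an immunocompromised patient.

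**3. How many patients could be affected?**

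Inputs: 108 participants, 36 per group (section 5, Sample Size Calculation). That figure reproduces for a chi-square test with 2 degrees of freedom, w = 0.3 and α = 0.05: power is 0.8037 at N = 108 and 0.7998 at N = 107. It is used here only for the group size.

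The share p of immunocompromised entrants is not in the documents. The assumed range is 0.5% to 5%.

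Expected number in Group 1 = 36 × p. Chance of at least one in Group 1 = 1 − (1 − p)^36.

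| Assumed p | Expected in Group 1 | Chance of at least one |
|---|---|---|
| 0.5% | 36 × 0.005 = 0.18 | 1 − 0.995^36 = 0.165 |
| 1% | 36 × 0.01 = 0.36 | 1 − 0.99^36 = 0.304 |
| 2% | 36 × 0.02 = 0.72 | 1 − 0.98^36 = 0.517 |
| 5% | 36 × 0.05 = 1.8 | 1 − 0.95^36 = 0.842 |

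In the whole trial: 108 × 0.005 = 0.54 to 108 × 0.05 = 5.4.

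**4. What would exclusion cost in recruitment?** Otherwise eligible patients needed to keep 108 = 108 / (1 − p).

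- p = 0.5%: 108 / 0.995 = 108.5, so 109, or 1 more.
- p = 5%: 108 / 0.95 = 113.7, so 114, or 6 more.

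**The case against.** The best counter-argument is that the protocol already answers the point. The Project Summary says that societies advise antibiotics in particular cases on evidence that is not strong, and section 3 says much the same directly after naming the exceptions. Read together, the stated uncertainty covers the exceptions as well as the general rule. That is a rationale, but a general one. It does not argue for withholding prophylaxis from immunocompromised patients, and the objective poses no question about them.

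A second argument is that the gap needs an unusual patient: well, afebrile, with a normal white count and graded ASA II. The documents do not say whom the guidelines count as immunocompromised, so whether this patient falls within the exception cannot be confirmed. This stands as a limit on size. The number is probably small, and the assumed prevalence has no anchor in the documents. It does not close the gap, because removal then depends on an undefined grading.

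A third is that the safeguards are substantial. Blood count, CRP and procalcitonin are measured after ERCP, treatment follows signs of infection and not fever alone, inpatients are assessed daily, the trial is open-label, and there is ethics approval and written consent. All of that is true and limits the harm. But treating an infection is not preventing one, and the reported exception is about prevention.

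Finally, the study flowchart is not reproduced in the available text, so its content could not be checked. The written eligibility list is complete without it.

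**Conclusion.** The concern holds, as a minor point of design. The protocol reports an exception for immunocompromised patients, removes them only in part, and allows one who meets the listed criteria to be allocated to saline without a justification or safeguard specific to that group. Confidence is medium, because the case depends on how ASA is graded and on whom the guidelines count as immunocompromised.

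If 0.5% to 5% of entrants are immunocompromised, about 0.2 to 1.8 controls would be affected, and the chance of at least one is 17% to 84%. These figures count entrants, not infections: the documents give no excess risk from which harm could be estimated. They also take Group 1 to hold the planned 36 patients.

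**What to change.** Add one exclusion criterion to section 6 (Eligibility): immunocompromised patients, defined by a list of conditions and a list of immunosuppressive medications, checked before allocation.

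The cost is one line with its definition and, under the assumed prevalence, 1 to 6 more otherwise eligible patients screened to keep 108. Generalisability narrows slightly, because the trial would no longer inform on immunocompromised patients. With 36 per group it could say almost nothing about them anyway.

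If the sponsor prefers to keep these patients, the alternative is to state why prophylaxis may be withheld from them and to add a safeguard specific to them.

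### Allocation by record number modulo 3 is deterministic and no concealment is described, so the trial is quasi-randomised and carries a risk of selection bias of unknown size and direction

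*Protocol*

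**What the plan says.** Section 5, Study Design, describes the trial as "Interventional Study, open-label, randomized controlled trial". Section 1, Project Summary, says of the patients: "They will be randomly assigned to one of three groups". Section 6, Methodology, under Interventions, gives the mechanism, which it labels simple randomisation: "the remainder of their record number divided by 3 determined the group allocation".

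The protocol mentions no generated sequence, central assignment or sealed envelopes. It does not say that the number is kept from the person who recruits, or that consent and eligibility are recorded before the remainder is read. Section 5, Data management and statistical analysis, mentions a second identifier, but for another purpose: "Each participant will be assigned a unique study identification number (ID) to maintain confidentiality".

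Three other provisions bear on the point:
- One inclusion criterion is "Good general condition, classified as ASA Physical Status I or II".
- One exclusion can be known only at the procedure: "Patients with duodenal perforation or failed ERCP due to inability to access the papilla".
- Section 3, Safety considerations, says that patients who, while awaiting ERCP, "develop signs of infection with a fever >37°C will be withdrawn from the study".

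**The concern.** Randomisation protects a comparison in two ways: the sequence is unpredictable, and whoever decides on entry cannot know the next assignment. The described rule supplies neither. Once the number is known, the arm is known.

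The control group receives saline and no antibiotic, and the trial is open-label. A clinician who is uneasy about a particular patient could therefore have a reason to act on that knowledge, for example by not approaching the patient, by deferring enrolment or by grading ASA class differently. Steering higher-risk patients away from control would lower the control fever rate and could hide a real benefit of prophylaxis. Steering the other way could create a false benefit. The trial has one objective, whether prophylaxis reduces infection, so either distortion falls on the main result. The planned p-values and RR intervals would not reflect it.

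**Working it through.** **1. Is there a random element?** The rule is arm = f(record number mod 3), with f fixed. Given the number, the arm is known with probability 1. Under concealed 1:1:1 simple randomisation, a guess is right with probability 1/3. The protocol text does not say which remainder goes to which group, but in an open-label trial the first treated patients reveal the mapping.

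**2. Does the meaning of record number matter?** If it is a hospital number, the arm can be read from the chart. If it is a consecutive study number, the arms rotate in fixed order and the next one is equally foreseeable. Both readings give a predictable allocation.

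**3. Where could foreknowledge act?** At entry: ASA grading, the indication for ERCP, the approach for consent and the timing of enrolment. After the arm is knowable: withdrawal for fever while awaiting ERCP, and removal for perforation or failed access. Absence of cholangitis is defined by numeric limits for temperature and white cell count, so it leaves little discretion.

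**4. Arm size.** The plan's sample size uses w = 0.3, 2 degrees of freedom, α = 0.05 and power 0.80. The noncentrality is N × w² = 108 × 0.09 = 9.72, which gives power 0.804, and 108 is the smallest N that reaches 0.80. The stated 108 (36 per group) reproduces. It is used here only to fix 36 per arm.

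**5. Illustration of size.** Assumptions, none of them a protocol statement about this trial:
- There is no true treatment effect.
- Half of candidates have 5% risk and half 18% (the ends of the infection range in section 3, Rationale and Background Information).
- A share s of the high-risk candidates whose number points to control is not enrolled.
- Each arm still reaches 36.

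High-risk share in control: h = 0.5(1 − s) / [0.5(1 − s) + 0.5]. Control rate = 0.18h + 0.05(1 − h). Rate in each antibiotic arm = 0.5 × 0.18 + 0.5 × 0.05 = 11.5%. RR is antibiotic versus control. The rejection rate comes from 100,000 simulated 3 × 2 chi-square tests at 0.05.

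| s | h | Control rate | RR | Rejection rate |
|---|---|---|---|---|
| 0% | 0.50 | 11.5% | 1.00 | 4.8% |
| 25% | 0.43 | 10.6% | 1.09 | 5.1% |
| 50% | 0.33 | 9.3% | 1.23 | 5.6% |
| 75% | 0.20 | 7.6% | 1.51 | 7.4% |
| 100% | 0.00 | 5.0% | 2.30 | 13.0% |

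**6. Effect of a few patients.** Replacing one 18%-risk patient with one 5%-risk patient shifts the expected rate of a 36-patient arm by (0.18 − 0.05)/36 = 0.36 percentage points. Three such swaps shift it by 3 × 0.36 = about 1.1 points.

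**The case against.** The strongest reply is that a remainder has no evident link to prognosis, so the groups should be comparable unless someone uses the foreknowledge, and nothing in the protocol shows that anyone did. The protocol is also silent on concealment rather than stating that there is none. Section 6, Quality assurance, refers to standard procedures for patient selection that are not reproduced. All of this stands, and it limits the finding to a risk. It does not rescue the label: the stated mechanism is not random, and nothing in the protocol keeps the number from recruiters. A separate analysis plan would not change this, because the protocol itself fixes the allocation method.

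A reader might infer more than the documents support:
- *That steering two or three patients would move the contrast by 6 to 8 points.* One patient is 1/36 = 2.8 points, but the larger figure needs each swap to replace a certain event with a certain non-event. Recruiters can select on risk, not on outcome, and on the assumed risks three swaps are worth about 1.1 points.
- *That signs of cholangitis are a matter of judgement at entry.* They are defined by numeric cut-offs.
- *That the number is a hospital number issued before consent.* This is likely from the wording, but it is not stated.
- *That the trial is biased, or wholly non-random.* Quasi-randomised is the accurate term, and the presence of bias cannot be established from the text.

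Timing is also a fair objection. The study window is December 2022 to December 2025, the rule is written in the past tense, and the reference list includes a January 2024 paper. The text was therefore completed at least 13 months into the window, and many patients may already be allocated.

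**Conclusion.** The point holds in this form: allocation is deterministic, it is labelled as simple randomisation in a trial described as randomised and controlled, and no concealment is described. That conclusion rests on the protocol's own wording and needs no numerical assumption.

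The consequence is a risk of selection bias whose presence, size and direction the documents cannot show. Under the stated assumptions, diverting half of the high-risk control candidates yields a spurious RR of about 1.23 with the rejection rate barely changed (5.6% against 4.8%). Diverting all of them yields about 2.30 with a rejection rate of about 13%. Diverting a quarter has little effect (RR 1.09, 5.1%). The need to change the plan comes from the allocation rule, not from these figures.

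**What to change.** **Patients still to be enrolled.** Replace the remainder rule with a computer-generated 1:1:1 sequence in permuted blocks of varying size. Hold it centrally or in sequentially numbered, opaque, sealed envelopes. Open each assignment only after consent and the protocol's existing eligibility checks are recorded, and before the first study treatment. Blocks also serve the planned 36 per group: in simulation, unrestricted simple randomisation of 108 gave exactly 36/36/36 in about 0.7% of runs, with a median smallest arm of 31.

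**Patients already allocated by remainder.**
- Describe this part as quasi-randomised wherever the protocol and reports now say randomised or simple randomisation.
- Report screened, eligible, enrolled and withdrawn counts by remainder (0, 1, 2).
- Keep all allocated patients in the primary analysis.
- Add a sensitivity analysis adjusted for baseline risk factors, and state that it cannot remove unmeasured selection.

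**Cost.** A protocol amendment, a generated list with a concealment procedure, some extra reporting, and a less favourable design label. If enrolment is complete, the new sequence no longer applies and only the relabelling, reporting and analysis steps remain.
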